Systematic reviews have shown that researchers have examined interventions for dementia carers who are primary caregivers, including some that focused on reducing their stress or promoting/preserving health. NIH-funded researchers have engaged in multi-site projects, Resources for Enhancing Alzheimer's Caregiver Health (REACH), since 1995, and have tested educational support groups, behavioral care, skills training programs, family-based interventions, environmental modifications, computer-based information, and communication services. All of the interventions were found to be superior to control conditions for women versus men and for caregivers with lower versus higher education. Positive outcomes include

fewer depressive and anxious symptoms, greater satisfaction, and a better sense of well-being. These studies, however, were limited to one phase of the caregiving career, primary caregiving; interventions were not tested in care partners or caretakers, who are believed to experience similar stress levels and deleterious effects on health. In addition, the interventions tested within the REACH projects did not include the implementation of biofeedback as a means for stress reduction or the teaching skills that constitute resourcefulness as proposed in this study.

Only one study examined biofeedback in caregivers of persons with dementia and it found that biofeedback was feasible and effective for stress management in family caregivers. The study was missing a control group and the sample was very small (N=32) and limited to in-home dementia caregivers whose care recipient attended a senior day care facility. However, systematic review of other intervention studies of dementia caregivers have described beneficial effects on caregiver health of such skills as cognitive reframing, problem-solving, self-management, and help-seeking, all of which are incorporated within resourcefulness training. Consistent with the personal (self-help) and social (help-seeking) skills taught during Resourcefulness Training, researchers have identified the need for interventions to assist dementia caregivers to seek out and mobilize social resources while enhancing personal coping effectiveness.

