INTERVENTION: Within two weeks of the first data collection session (including study scales and HRV data collection), carers within each of the three caregiving phases (caregivers, care partners, and caretakers) will be randomly assigned using a computer program to one of three treatment groups: 1) Self-management (SM) need, 2) Self-management (SM) preference, or 3) attention control. The SM-need group will receive a self-management intervention tailored to meet their need for resourcefulness training (RT) or biofeedback (BF) as

HRP- 503SBER	TEMPLATE: SBER Protocol		
Approved:	01/2019	Prior Version:	05/2018

determined by whichever baseline cut score is lower, the Resourcefulness Scale or the SDNN parameter for age and gender. Carers randomly assigned to the SM-preference will choose to do RT or BF according to their personal preference. However, we will use minimization methods for group assignment to ensure equivalent representation across the three treatment groups, and factors likely to affect variables of interest, including carer age, gender, and race/ethnicity, in order to insure demographic similarity.

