Prior to testing the study aims, demographic profiles for caregivers, care partners, and caretakers will be created through univariate descriptive statistics, including means, standard deviations, and range of scores, and will be used to assess continuous data; frequencies and percentages will be used to describe categorical data. We will track the health conditions and the life events of all carers and dementia symptoms, level of care, and health rating of the care recipient for those who are not bereaved. However, the primary aim (**Aim 1**) is to test the effects of health self-management interventions (RT or BF) delivered based on need (i.e., cut score) or preference (i.e., personal choice) of dementia carers who have transitioned within six months to a new phase in the caregiving career (to at-home caregiver, to care partner with a facility, or to caretaker following the death of care recipient). **Aim 1** is to compare carers who are randomly assigned to the need (SM-need, preference (SM-preference) group, or an attention control condition over 3 time points (baseline, 6 months, and 12 months) on carer responses (i.e., perceived stress, depressive cognitions, and negative emotions) (**Aim 1a**), and health outcomes (health risk, and physical and mental health) (**Aim 1b**). **Aim 2** will focus on comparing caregivers, care partners, and caretakers. For **Aims 2a and 2b**, we will determine whether differences exist among caregivers, caregivers, care partners, and caretakers in carer responses (**2a**) and health outcomes (**2b**) over time. For all analyses, we will control for the effects of three covariates: months in caregiver, care partner, or caretaker role, dementia symptom severity, and caregiving demands.

For both study aims, we will use a 3 group by 3-time point Repeated Measures Analysis of Variance (RMANOVA), as well as 3 group by 3-time point Repeated Measures Analyses of

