Covariance (RMANCOVA) to control for the three covariates on carer responses (i.e., perceived stress, depressive cognitions, and negative emotions) (**Aim 1a and Aim 2a**) and health outcomes (health risk, and physical and mental health) (**Aim 1b and 2b**). We will use both analyses in a two-step process: first, we will use RMANOVA to determine if mean differences exist among the 3 groups over 3 time points. If we find mean differences, for the second step we will run RMANCOVA to identify how the covariates impact the initial findings. This controls for any confounding effects of the covariates on the repeated measures models and will also allow us to determine how much of an impact the covariates have on carer responses and health outcomes.

The RMANOVA and RMANCOVA will allow us to not only assess mean differences across time, group differences, and the interaction of time X group in order to test the trend of the means over time across the SM- need, SM-preference, and attention control condition in **Aim 1** and caregiver vs. care partner vs. caretaker in **Aim 2**. The RMANOVA and RMANCOVA not only can be used to determine if there are mean differences across the three time periods, but can also utilize orthogonal polynomial contrasts to determine whether linear and quadratic trends of the means across time are significant.

Confidentiality of Data

1. To maintain the confidentiality of the data:

I will use a unique study identifier to code individuals' identifiable data and will store the master list separate from the study data..

Other (please explain)

Provide a plan to destroy identifiers including how and when.

Identifiers in the Screening log (Box.com) and Contact Form (REDCap and CWRU BOX) will be destroyed after data collection is complete, and before the study is closed, by deleting the files.

How are you storing your electronic data?

UH Redcap

CWRU Redcap

Secure Research Environment (SRE)

CWRU Box

OnCore

UH Secure Network Drive

CWRU Secure Network Drive

Other - List storage method and provide justification:

2. Storage location of the paper research data and documents, if applicable:

Paper research data and documents will be stored in a double-locked secure environment in the following location:

France Payne Bolton School of Nursing – Health Research Campus study office

3. Will data be shared?
 Yes
1. List the exact data elements that will be shared:
2. Describe how data will be sent:
 No
 N/A

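### The Aim 2 model omits randomised arm, so a treatment effect that differs by caregiving phase would appear as a different course by phase, and no planned term would detect it

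*Combined protocol and SAP*

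**What the plan says.** All references are to the combined protocol and SAP.

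- **Aim 2 comparison (Data Analysis Plan).** Aim 2 "will focus on comparing caregivers, care partners, and caretakers" on carer responses and health outcomes over time.
- **Model (same section).** For both aims, "we will use a 3 group by 3-time point Repeated Measures Analysis of Variance (RMANOVA"), followed by a covariance version if mean differences are found. In the time-by-group test the group is treatment arm for Aim 1 and "caregiver vs. care partner vs. caretaker in" Aim 2.
- **Covariates (same section).** The covariate statement covers every analysis: "we will control for the effects of three covariates: months in caregiver, care partner, or caretaker role, dementia symptom severity, and caregiving demands". Arm is not listed. No arm-by-phase term is given, and Aim 2 is not restricted to one arm.
- **Allocation (Study Design/Procedures, INTERVENTION).** "carers within each of the three caregiving phases (caregivers, care partners, and caretakers) will be randomly assigned using a computer program" to SM-need, SM-preference or attention control, and "we will use minimization methods for group assignment to ensure equivalent representation across the three treatment groups". No ratio is printed.
- **Timing (same section).** The two SM arms are trained and practise between T1 and T2, and may carry on to T3. Attention control gets diversional activities over the same period.
- **Hypothesis (Objectives).** Carers given either intervention are expected to do better than attention control whatever their phase.
- **Purpose of the phase comparison (end of Background).** To explore how carers in the three phases differ in their responses to a recent transition and in health outcomes over time.

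**The concern.** T1 precedes the intervention. T2 and T3 do not, and most carers in every phase will by then have been trained in resourcefulness or biofeedback. Each phase's T2 and T3 means therefore mix its course under attention control with its response to training, and the Aim 2 model has nothing to separate the two. The covariance step does not help, because arm is not one of its covariates.

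Two things are at stake. A significant phase-by-time result could reflect how carers in different phases react to the transition, or how well the training works in each phase, and the planned output would not show which. In addition, the hypothesis that the benefit holds in every phase is stated but never tested, since the Aim 1 model has no phase term and the Aim 2 model has no arm term.

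An unequal response is possible on the protocol's own account. The examples given to resourcefulness-training participants vary with caregiving type. The mix of resourcefulness training and biofeedback is set by baseline scores or by choice, so it may vary by phase.

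**Working it through.** The plan prints no figure on this point. The target of 350 carries no stated alpha, power, effect size or dropout, so there is nothing to reproduce first.

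**Inputs**

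- Total 350 (Number of Research Participants).
- Three arms. Equal allocation is assumed from the stated aim of equivalent arms, so the active share is p = 2/3.
- Equal phase sizes (assumed): 350/3 = 116.7 per phase and 350/9 = 38.9 per phase-by-arm cell.
- SD 1, correlation between time points 0.5 or 0.7, two-sided alpha 0.05, no dropout (all assumed).

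**Step 1: algebra.** Let a_k be the T1-T2 change in phase k under attention control, and d_k the effect of active training relative to attention control. Then

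observed change in phase k = a_k + p x d_k

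observed phase difference in change = (a_1 - a_2) + p x (d_1 - d_2)

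- Equal effects, d = 0.5 SD everywhere: the second term is 0, so the phase contrast is unbiased. Each phase's own change still moves by (2/3) x 0.5 = 0.33 SD from its attention-control course.
- Effects differing by 0.3 SD: (2/3) x 0.3 = 0.20 SD appears as a phase difference.
- Effects differing by 0.5 SD: (2/3) x 0.5 = 0.33 SD.

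**Step 2: the planned test.** The 3 phase by 3 time interaction F test was simulated (2,000 runs, 116 per phase, compound symmetry). The attention-control course was identical in all phases, and the treatment effect was present at T2 and T3.

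| Effect in the three phases (SD) | Rejection, correlation 0.5 | Rejection, correlation 0.7 |
|---|---|---|
| 0, 0, 0 | 5% | 5% |
| 0.5, 0.5, 0.5 | 5% | 4% |
| 0.3, 0, 0 | 31% | 52% |
| 0.5, 0.25, 0 | 63% | 85% |
| 0.5, 0, 0 | 75% | 96% |

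The same test within attention control alone (39 per phase) rejected in 4% to 6% of runs in every scenario.

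**Step 3: precision of the attention-control comparison.** The pairwise phase difference in T1-T2 change detectable with 80% power is (1.960 + 0.842) x sqrt(2(1 - rho)) x sqrt(2/n).

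- All carers, n = 116.7: 0.37 SD (correlation 0.5) or 0.28 SD (0.7).
- Attention control only, n = 38.9: 0.64 SD or 0.49 SD.

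**Step 4: precision of the interaction.** Comparing the treatment effect on change between two phases has standard error sqrt(2(1 - rho)) x sqrt(2 x (1/77.8 + 1/38.9)), where 77.8 = 116.7 x 2/3. At correlation 0.5 this is sqrt(0.0771) = 0.278, so the detectable difference is 2.802 x 0.278 = 0.78 SD. At correlation 0.7 it is 0.78 x sqrt(0.6) = 0.60 SD.

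**The case against.** The strongest reply is that the design already deals with the ordinary problem. Randomisation is within phase, so arm is not confounded with phase, and the protocol expects benefit in every phase. If that benefit is of equal size, the phase-by-time test is valid as planned. Nor does Aim 2 say that it estimates a course without intervention: it asks whether phases differ over time, and an average over a balanced arm mix is a legitimate answer. This stands. It is why the all-carer comparison should remain the main result.

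The evidence for unequal response is also thin. The Background remark that "interventions were not tested in care partners or caretakers" concerns an earlier multi-site programme that included neither biofeedback nor resourcefulness teaching. Untested is not the same as different. This stands too: the documents show that a differential effect is possible, not that it is likely.

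A reader might infer that attention control shows the untreated course and should lead. The documents do not support that. Attention-control carers also have a training session, diversional activities, a 28-day workbook and weekly contact, so that arm shows the course without resourcefulness training or biofeedback, not without attention. Leading with it would raise the detectable difference from 0.37 to 0.64 SD at correlation 0.5, which is a substantial loss.

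The reply does not cover the missing term. Balance removes a common effect but not a differential one, and the assumption that the effect is common is itself an untested hypothesis of the trial.

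**Conclusion.** The point holds in a limited form. As planned, Aim 2 cannot separate a phase difference in response to transition from a phase difference in response to treatment, and nothing in the plan tests whether treatment response varies by phase. The distortion of the phase contrast is two-thirds of any between-phase difference in effect: 0.20 to 0.33 SD for assumed differences of 0.3 to 0.5 SD, and zero if the effect is equal. Under equal effects, only each phase's own trend is shifted.

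This rests on equal allocation, which is inferred. The effect sizes and correlations are illustrative, since the documents give none.

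Two stronger readings should be resisted. A reader might infer that the Aim 2 phase-by-time result is bound to be false, but an equal effect leaves it at its nominal error rate. A reader might also infer that only the T1 comparison can be interpreted. T1 is free of the issue in every case, but the T2 and T3 phase contrasts are also unaffected if effects are equal. Assignment is recorded as well, so the question can be examined; it is just not prespecified.

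**What to change.** In the Data Analysis Plan, for Aim 2:

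1. Add arm, arm-by-time, arm-by-phase and arm-by-phase-by-time to the model. Arm or arm-by-time alone would not separate a differential effect.
2. Keep the phase-by-time comparison on all carers as the main Aim 2 result, averaged over arms, and say that it describes the trial's arm mix.
3. Report the arm-by-phase-by-time test with estimates and intervals. This also addresses the stated hypothesis of benefit in every phase.
4. Prespecify the phase courses within attention control as a supporting analysis, described as the course without resourcefulness training or biofeedback.
5. Use all carers for the T1 phase comparison.

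**Cost.** Plan wording and a few model terms on data already collected; recruitment, participant burden and Aim 1 do not change. The three-way term has low power (detectable between-phase difference in effect about 0.60 to 0.78 SD under the assumptions above), so a non-significant result should not be read as equal effects. The attention-control courses rest on about 39 carers per phase before dropout and will have wide intervals.

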The **second aim** is to determine whether differences exist among caregivers, care partners, and caretakers in carer responses (**2a**) and health outcomes (**2b**) over time. All carers will complete measures of caregiving responses and health outcomes at baseline (T1), 6 months (T2), and 12 months (T3). The four-week interventions will occur between T1 and T2 data points. Carers may use the intervention as often as they wish (i.e., self-tailoring); dosing and fidelity will be measured. Repeated measures bivariate and multivariate analyses will address the study aims while controlling for dementia symptom severity and caregiving demands.

Background

Directions: Describe the relevant prior experience and gaps in current knowledge describing how it will add to existing knowledge. Include any relevant preliminary data.

Dementia is the most under recognized health crisis of the 21st century, with over 46 million people worldwide living with dementia, a number that is expected to reach 131.5 million by 2050.⁴ In the United States, family members provide care for over 5.4 million elders with some form of dementia. Regardless of cause, dementia has a slow, progressive, fairly predictable downward course, with losses in mental and physical functioning that generate negative **carer responses** (i.e., perceived stress, depressive cognitions, negative emotions) and may seriously compromise the family carer's health risks and physical and mental health (i.e., **health outcomes**). Research shows that within six months of a transition to a new caregiving phase (i.e., from caregiver, to care partner, to caretaker), the health of family carers shows evidence of substantial decline. Although researchers have identified factors occurring throughout the caregiving career that may adversely affect the carer's health, interventions to promote health self-management by reducing negative caregiving responses have not been tested in carers who have recently transitioned into the role of caregiver, care partner, or caretaker. Consistent with

the Precision Medicine Initiative, which presents an innovative model that accounts for individual differences and empowers health care recipients (i.e., family carers) to participate actively in health care decisions, sustainable self-management interventions should be designed and tailored to match the carer's needs and preferences and then tested with randomized, controlled trials.

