The data collection for caregivers sampled involves three structured face-to-face sessions with data collectors, each lasting typically 60-90 minutes. Data will be collected at baseline (T1), at 4-6 months (T2) after the 4-week intervention, and at 12-4-6 months later (T3). The data collection includes measures of carer health conditions, carer life events, health rating of care recipient, resourcefulness (including financial resourcefulness), dementia symptom severity, caregiving demands, carer responses to perceived stress, depressive cognitions, negative emotions, carer health outcomes, caregiving effort scales, and COVID-19 questions comprising the 158-225 item questionnaire (bereaved caretakers are not asked all study measures since they are no longer actively caring for their family member). Demographic information will also be collected (e.g. occupation, annual income, education, and questions about the care recipient such as age, number of years diagnosed with dementia, specific diagnoses, and questions related to the participant's caring of their family member with dementia). The third, and final, data collection session involves the additional measure of an Intervention Evaluation Questionnaire that will ask participants for feedback regarding the intervention they received.

The table below shows which study instruments are administered at each time point:

Data Collection Instrument	Baseline / T1	4-6 months post-intervention / T2	12-4-6 months post-T2 / T3
Demographic and Descriptive Data*	X	X	X
Health Rating of Elder Care Recipient**	X	X	X
Cultural Justification for Caregiving	X	X	X
Resourcefulness Scale	X	X	X
Financial Resourcefulness	X		
Revised Social Readjustment Rating Scale	X	X	X
Revised Memory and Behavior Problems Checklist**	X	X	X
Perceived Stress Scale	X	X	X
Depressive Cognition Scale	X	X	X
Negative Emotions Checklist	X	X	X
Caregiver Appraisal of Functional Capacity**	X	X	X
Health Risk Behavior Scale	X	X	X
PROMIS Global Health Measures	X	X	X

HRP-503SBER	TEMPLATE: SBER Protocol		
Approved:	01/2019	Prior Version:	05/2018

Caregiving Effort Scales	X	X	X
Financial Stress	X		
COVID-19 Questions	X	X	X
Intervention Evaluation Questionnaire			X
Heart Rate Variability	X	X	X

* Questions 7-13 of the Demographics will NOT be asked to caretakers.

** These scales will NOT be asked to caretakers.

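### The adjusted step for both aims needs a dementia-severity covariate (and, by inference, a demands covariate) that caretakers lack by design, so as written it cannot include that phase

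*Combined protocol and SAP*

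**What the plan says.** The Objectives section promises adjustment in general terms: "Repeated measures bivariate and multivariate analyses will address the study aims while controlling for dementia symptom severity and caregiving demands". The Data Analysis Plan adds a third covariate and says of every analysis: "we will control for the effects of three covariates: months in caregiver, care partner, or caretaker role, dementia symptom severity, and caregiving demands".

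The adjustment comes in two steps for both aims. An unadjusted RMANOVA compares three groups at three time points. Then: "If we find mean differences, for the second step we will run RMANCOVA to identify how the covariates impact the initial findings". The groups are the three arms for Aim 1 and the three phases (caregiver, care partner, caretaker) for Aim 2. The outcomes are the carer responses (1a, 2a) and the health outcomes (1b, 2b).

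The data collection text under Study Design/Procedures says that "bereaved caretakers are not asked all study measures since they are no longer actively caring for their family member". In the instrument table that follows, the "Revised Memory and Behavior Problems Checklist" and the "Caregiver Appraisal of Functional Capacity" carry a double asterisk, and the footnote reads "These scales will NOT be asked to caretakers". The Data Analysis Plan agrees with this: it will track "dementia symptoms, level of care, and health rating of the care recipient for those who are not bereaved".

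**The concern.** A model cannot adjust for a covariate that one group never has. Here the covariate is absent for the whole of one phase, and phase is the grouping factor of Aim 2. The plan gives no substitute or retrospective measure, no rule for missing covariates, no reduced covariate set for caretakers and no restriction of the adjusted model to two phases.

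Three things are at stake when step 2 runs:

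- **Aim 2.** The adjusted three-phase comparison, which is the purpose of the aim, cannot be fitted.
- **Aim 1.** Carers are randomised within all three phases and the hypothesis claims benefit whatever the phase, but the adjusted result would describe non-bereaved carers only.
- **Reading step 2 against step 1.** The second step is meant to show what the covariates do to the first result. If the population changes at the same time, the two effects cannot be separated.

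If the plan stays silent, the handling of caretakers would be chosen after the step 1 results are known.

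**Working it through.** The plan gives no figure to reproduce on this point: no alpha, power, effect size or standard deviation. The check is mainly structural, with a range for the size.

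**1. Is each covariate available in each phase?**

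| Covariate | Caregiver, care partner | Caretaker | Basis |
|---|---|---|---|
| Months in role | Yes | Yes | Eligibility depends on when the carer entered the phase |
| Dementia symptom severity | Yes | No | Data Analysis Plan limits symptom tracking to non-bereaved carers; the footnote withholds the behaviour checklist |
| Caregiving demands | Yes | No (inferred) | Footnote withholds the functional-capacity scale |

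The documents do not state which scale measures which covariate. The match is inferred from the scale names, the order in which constructs are listed in the data collection text, and the titles of the two source references. Severity does not depend on that inference, because the Data Analysis Plan makes the restriction in words. One absent covariate is enough to remove a carer from a complete-case model.

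**2. What is left in step 2?** Assume complete-case handling, and for illustration phases of 117, 117 and 116 in the target sample of 350. Step 1 uses 350 carers. Step 2 uses 117 + 117 = 234, with no caretakers. For Aim 2 this leaves caregiver versus care partner; both contrasts involving caretakers are not estimable.

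Imputation does not solve this. Absence coincides exactly with phase, so no caretaker supplies a value to impute from, and any imputed value is extrapolated from the other phases.

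**3. Precision of the Aim 1 arm contrasts.** With residual variance held fixed, SE ratio = sqrt(1 / (1 − share)), where share is the caretakers' share of the sample.

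**4. Shift from the change of population.** With arms balanced within phase:

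- step 1 effect = share × (effect in caretakers) + (1 − share) × (effect in non-bereaved)
- step 2 effect = effect in non-bereaved
- difference = share × (effect in non-bereaved − effect in caretakers)

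The documents support no value for the difference in effects; 0.3 SD is assumed below.

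| Assumed caretaker share of 350 | Lost | Left | SE ratio | Shift at 0.3 SD |
|---|---|---|---|---|
| 20% | 70 | 280 | sqrt(1/0.8) = 1.118 | 0.2 × 0.3 = 0.06 SD |
| 33.3% | 117 | 233 | sqrt(1/0.667) = 1.225 | 0.333 × 0.3 = 0.10 SD |
| 40% | 140 | 210 | sqrt(1/0.6) = 1.291 | 0.4 × 0.3 = 0.12 SD |

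**5. Check of the alternative model.** A simulation of 1,000 trials used one time point, phases of 117/117/116, covariates with no effect on outcome, and an arm effect of 0.3 SD in non-bereaved carers and 0 in caretakers.

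| Model | n | Mean estimate (SD) | SE |
|---|---|---|---|
| Unadjusted step 1 | 350 | 0.199 | 0.131 |
| Complete-case step 2 | 234 | 0.299 | 0.160 |
| Phase in the model, covariates centred within phase, zero for caretakers | 350 | 0.198 | 0.131 |

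The move from 0.199 to 0.299 would be read as a covariate effect, although the covariates do nothing. This illustrates the formula in item 4 under the same assumed effects; it is not separate evidence that such a difference exists.

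**The case against.** - **The demands covariate is not firmly established.** The instrument pack is not part of the documents, and the Caregiving Effort Scales carry no asterisk, so caretakers do answer one caregiving scale. This stands as a limit on the demands half. The data collection text lists the effort scales separately from demands, however, and they would not supply dementia severity, which is enough for the conclusion.
- **Step 1 is intact.** It compares the arms in all three phases, and randomisation makes that comparison valid without covariates. Step 2 is conditional. This stands: the main damage is to adjusted Aim 2, and the unadjusted Aim 1 comparison survives. But step 2 runs exactly when there is a difference to explain, and the plan relies on it to deal with confounding.
- **Complete-case handling is assumed, and an Aim 2 model with no caretaker rows would be noticed.** Both are true. Noticing the failure does not supply a rule, and in Aim 1 the model would still run and give arm contrasts.
- **The sizes rest on assumptions.** This stands. The shift is zero if the effect is the same in every phase. The SE ratios compare step 2 with step 1 as if the covariates explained nothing. With an assumed R-squared of 0.2 the ratio is sqrt(0.8/0.8) = 1.00 at a 20% share and sqrt(0.8/0.667) = 1.10 at one third.
- **The proposed Aim 1 model is one option among several.** Also true. Restricting the severity and demands adjustment to non-bereaved carers, and saying so, would be coherent, but it leaves randomised caretakers out of the adjusted result.

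**Conclusion.** The concern holds. The adjusted three-phase model for Aim 2 cannot be fitted from the data the protocol collects, and the adjusted Aim 1 model cannot include caretakers as written. The severity covariate alone establishes this; the demands covariate very likely adds to it.

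The structural loss does not depend on sample size. With complete-case handling, all caretakers leave step 2, and two of the three adjusted Aim 2 contrasts go with them. The Aim 1 figures (70 to 140 carers lost, standard errors about 12% to 29% larger) depend on the assumed phase split and on fixed residual variance. The 0.06 to 0.12 SD shift is an illustration under an assumed difference in effects. The unadjusted first step is sound in this respect. The plan should be corrected before any comparative analysis, because the specified model does not match the specified data.

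**What to change.** Amend the Data Analysis Plan as follows.

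1. **Name the instruments** that supply dementia symptom severity and caregiving demands, and state that their T1 values are used. The plan does not say whether the covariates are baseline or time-varying. T1 values also cover carers who are bereaved during follow-up.
2. **Aim 1.** Include phase and phase by time in the adjusted model. Centre T1 severity and demands within each non-bereaved phase and set them to zero for caretakers. All randomised carers then stay in, and the phase term absorbs the level difference.
3. **Aim 2.** In the three-phase comparison, adjust only for the planned covariate that is defined in every phase, months in role. Limit adjustment for severity and demands to caregiver versus care partner.
4. **Both aims.** Run steps 1 and 2 of each comparison on the same carers, so that a change between them reflects the covariates and not the population.
5. **Align the Objectives and the sentence covering all analyses** with these rules.

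The cost is plan wording; no new data are needed. The three-phase comparison could no longer be described as adjusted for severity and demands, but the data cannot support that description now.
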